grade 3 or higher pneumonitis, grade 3 or higher nephritis, grade 3 or higher transaminitis, or any grade myocarditis in 2 out of the first 6 patients in the AML arm of the study. In this case, the upper 90% one-sided CI bound for 2 patients with SAEs within 6 patients would be 66.7%, consistent with an excessive rate of toxicity.

- The fraction of patients experiencing grade 3 or higher colitis/diarrhea, grade 3 or higher pneumonitis, grade 3 or higher nephritis, grade 3 or higher transaminitis, or any grade myocarditis exceeds 40%, at any time during study implementation beyond the first 6 patients in the AML arm.

If the study is stopped due to activation of the above rules, the safety data will be examined by the Sponsor in consultation with investigators in order to determine how to proceed or whether to discontinue the study at large.

Note: Dose modifications for HMA-related (known/expected) toxicities -for either azacitidine or decitabine- in AML patients will be based on the respective US Prescribing Information for these products. These documents are included as Appendices 12.1 and 12.2.

Procedures

After signing the informed consent, patients will enter the 28-day Screening period. At the baseline visit (Day -2), all pretreatment screening procedures/assessments must be completed, review of inclusion/exclusion criteria (including specific tumor histologic type verification, [e.g., TNBC]), and review of laboratory and tissue pathology results confirmed prior to enrollment and the first GM-CSF injection.

Patients will then enter the open-label treatment period which is approximately 111 weeks (777 days; 2.13 years) in duration; the last galinpepimut-S administration would occur at 84 weeks (day 588 days; 1.61 years).

Patients will be treated until progression, death, unacceptable toxicity (including activation of the stopping rules in either the solid tumor arms or the AML arm), or completion of 2 years of therapy with pembrolizumab, whichever occurs first.

A safety follow-up period will occur 30 days after the last administration of study drug. A follow-up phone call for serious adverse events will occur 90 days after the last dose of pembrolizumab or 30 days following cessation of study treatment if the patient begins new anticancer therapy, whichever is earlier. If the patient initiates new anticancer therapy, this must be reported by the investigator.

For a full list of study procedures, including the timing of each procedure, please refer to [Section](#) and the Schedule of Assessments in [Table 8](#).

Estimated Study Duration:	Maximum study treatment duration is approximately 111 weeks (777 days; 2.13 years), during which the last galinpepimut-S administration would occur at 84 weeks (day 588 days; 1.61 years) – all time measurements assume t-zero the date of first galinpepimut-S administration, except specifically for safety, t-zero assumes the date of first GM-CSF administration (day -2 of the entire protocol schedule).
Efficacy Assessments:	Signal response for each a priori statistically defined clinical outcome (ORR per RECIST 1.1) for all solid tumor types or other appropriate instrument scales, such as attainment of morphologic CR in AML patients. In addition to RECIST 1.1, all scans will be read according to iRECIST immune response consensus guideline (Seymour et al, 2017) to ensure that patients are not discontinued from therapy due to the phenomenon of tumor “pseudoprogression”, and clinical decisions will be based on iRECIST (Hodi et al, 2016).
Exploratory Assessments:	ORR per iRECIST in patients in the solid tumor arms and the frequency (rate) of achievement of MRD negativity in patients in the AML arm will be evaluated as exploratory endpoints. All patients enrolled in the study will be followed and assessed for PFS and OS, according to the intent-to-treat (ITT) principle. Specifically for OS, patients who complete the protocol-specified study treatment period or patients who discontinue early will enter an off treatment follow-up period to assess OS, with regular assessments every 3 months until study closure (defined as up to 2 years and 6 weeks, i.e., 111 weeks after the first galinpepimut-S administration given to the last patient

enrolled into the study, which corresponds to 2 years after the first injection of pembrolizumab).

This study will also assess the effect of the study treatment on readouts of immunologic tests in PB samples, as well as presence and density of immune cell infiltrates within the tumor stroma (or BM in AML patients) using at least one post-therapy tumor biopsy (and comparing the findings with those at baseline, i.e., prior to initiation of treatment). Details are provided in [Section 6.3](#).

Safety Assessments:

At each galinepimut-S administration visit the investigator will review concomitant medications, AEs, ECOG performance status score, vital signs (including body temperature, systolic and diastolic blood pressure [BP], heart rate, and respiratory rate; and weight). All blood samples will be collected before galinepimut-S and/or pembrolizumab administration (Day 1 of each cycle). Blood samples for complete blood count (CBC) with differential and platelet count and serum chemistry, will also be collected prior to the administration of GM-CSF at Day - 2 of each cycle whereby galinepimut-S is also co-administered. In addition to the blood samples collected for safety, blood samples will be collected for exploratory investigations on immune reactivity against the tumor.

Safety assessments will be conducted at every visit. The EOT visit will occur 30 days after the last pembrolizumab injection. A follow-up phone call for serious adverse events (SAEs) will occur 90 days after the last dose of pembrolizumab or 30 days following cessation of study treatment if the patient begins new anticancer therapy, whichever is earlier.

Toxicity will be graded in accordance with CTCAE v5.0 developed by the NCI

(https://ctep.cancer.gov/protocolDevelopment/electronic_applications/docs/CTCAE_v5_Quick_Reference_5x7.pdf).

Details regarding mitigation steps if AEs occur during drug administration (e.g., injection site reactions [ISRs]) post-galinepimut-S SC administration (when administered as monotherapy during the first 2 administrations, as well as subsequently, i.e., in combination with pembrolizumab IV infusion), as well as infusion related reactions (IRR) to pembrolizumab IV (when given in combination with galinepimut-S SC) are included in [Section 5.3.6](#).

**Statistical
Considerations:**

Sample Size: Approximately 90 patients will be enrolled in the study. The planned number of patients within each tumor-specific cohort is as follows: CRC (N = 20), OvC (N = 20), SCLC (N = 20), TNBC (N = 15), and AML (N = 15). This study uses a Bayesian monitoring approach to guide decision-making using data on the primary efficacy endpoint (ORR for patients in the solid tumor arms and rate of achievement of CR/CRi/CRp in patients in the AML arm) within each tumor-specific cohort. If the data provide high confidence that the true ORR (or CR/CRi/CRp rate for AML) exceeds a minimal clinically meaningful level or threshold, then the results would support continued development (a “Go” decision) for that cohort. If the data suggest that the true ORR (or CR/CRi/CRp rate for AML) is unlikely to meet the desired level of clinical activity, then the results would support a decision to halt further continuation of accrual (a “Stop” decision) for that cohort. This approach is

based on the decision-making framework of [Lalonde et al, 2007](#) and [Frewer et al, 2016](#).

For each tumor type test, the minimal clinically meaningful level of any given ORR (or CR/CRi/CRp rate for AML) value/result is defined by the “lower reference value” (LRV), and the desired level of clinical activity is defined by the “target value” (TV). The LRV and TV for each tumor type are determined by a synthesis of medical opinion, evidence from the literature, or data from other compounds being developed in the same area. These values are as follows: CRC LRV=10%, TV=20%; OvC LRV=10%, TV=20%; SCLC LRV=30%, TV=40%; TNBC LRV=15%, TV=25%; AML LRV=15%, TV=25%.

Enrollment in a cohort may be stopped for futility prior to reaching the planned sample size if there is a high predicted probability of a Stop decision at the planned sample size. Enrollment in a cohort may be increased with approximately 10 additional patients beyond the planned sample size if the sponsor determines that further data is needed to clarify the safety or efficacy signals for a Go/No-Go decision.

Based on the performance characteristics computed and described in the statistical section of the protocol, the sample sizes are adequate to address the study’s objectives. No formal statistical power calculations to determine sample size were performed.

Statistical Methods:

Analysis Sets

- The full analysis set (FAS) comprises all patients who are assigned to receive study treatment as per the intent-to-treat (ITT) principle, regardless of whether or

not they subsequently go on to receive study treatment or whether they deviate from the protocol in any major way.

- The modified intent-to-treat (mITT) set comprises all patients who are assigned to receive study treatment and have at least 1 post-baseline efficacy assessment (RECIST 1.1), even if they deviate from the protocol in any major way. The mITT will also include any patient that goes off study treatment because of clinical progression prior to the first scheduled per-protocol scan.
- The safety analysis set comprises all patients who receive any amount of study drug.
- The per-protocol set (PPS) comprises all patients who are assigned to receive study treatment, receive at least 1 injection of study treatment, have at least 1 post-baseline efficacy assessment (RECIST 1.1), and do not deviate from the protocol in any major way

All efficacy analyses will be based on the FAS and will also be conducted on the mITT set and PPS for exploratory purposes. The study's primary objective will be judged on the basis of the analysis of ORR. For CRC patients, only those with MSS and MSI-L will be included in the primary efficacy analysis. The safety analyses will be based on the safety analysis set and will group patients according to treatment actually received. Secondary and exploratory efficacy analyses will be performed on the FAS as well as on the mITT set and PPS for exploratory purposes.

Analysis of Primary Efficacy Endpoint: For each tumor-specific cohort, a Bayesian approach with non-informative

Jeffreys prior beta distribution with parameters $a = 0.5$ and $b = 0.5$ will be used to estimate the ORR (or CR/CRi/CRp rate in AML) and its 95% credible interval based on the posterior distribution.

At the time of analysis, within each tumor-specific cohort, the prior distribution will be updated with all available data from the evaluable patients to obtain the posterior distribution of the true ORR. The posterior probabilities that ORR (or CR/CRi/CRp rate in AML) exceeds TV and LRV will be reported for each cohort. A high posterior probability that $ORR > LRV$ will support a “Go” decision to continue development in the cohort, and a low posterior probability that $ORR > TV$ will support a “Stop” decision to halt development in the cohort. A “Consider” decision results if neither a Stop nor a Go decision can be made. The specific criteria for making a Stop, Consider, or Go decision within each tumor-specific cohort are derived using the following acceptable risks:

- 10% false stop risk: maximum acceptable probability that $ORR > TV$ given that a Stop decision is made.
- 20% false go risk: maximum acceptable probability that $ORR \leq LRV$ given that a Go decision is made

Before reaching the planned sample size in a cohort, the posterior probabilities will be updated continuously after each patient (or group of patients) and will be used to determine, within each cohort, the predictive probability of eventually reaching a Stop decision at the planned sample size. If this predictive probability is $\geq 80\%$, then enrollment in that cohort may be stopped early for futility.

Stop/Go and futility decision criteria are non-binding and may be regarded as guidance and information to be integrated with a full medical review of safety and efficacy data observed at the time of analysis in determining the next course of action. No tests of statistical significance are planned.

CRC

Given a sample size of 20 patients in the CRC (third/fourth line) group, where TV = 20% and LRV = 10%, the decision criteria are as follows: Go if ≥ 4 responses observed (20%); Stop if ≤ 1 responses observed (5%). With these criteria, there is a 59% probability of a Go decision and 7% probability of a Stop decision if the true ORR is 20%, and there is a 13% probability of a Go decision and 39% probability of a Stop decision if the true ORR is 10%.

OvC

The same sample size, TV, LRV, decision criteria, and probability statements as the CRC group apply.

SCLC

Given a sample size of 20 patients in SCLC group, where TV = 40% and LRV = 30%, the decision criteria are as follows: Go if ≥ 8 responses observed (40%); Stop if ≤ 5 responses observed (20%). With these criteria, there is a 58% probability of a Go decision and 13% probability of a Stop decision if the true ORR is 40%, and there is a 23% probability of a Go decision and 42% probability of a Stop decision if the true ORR is 30%.

TNBC

Given a sample size of 15 patients in the triple negative breast cancer group, where TV=25% and LRV=15%, the decision

criteria are as follows: Go if ≥ 4 responses observed (27%); Stop if ≤ 1 responses observed (7%). With these criteria, there is a 54% probability of a Go decision and 8% probability of a Stop decision if the true ORR is 25%, and there is a 18% probability of a Go decision and 32% probability of a Stop decision if the true ORR is 15%.

AML

The same sample size, TV, LRV, decision criteria, and probability statements as the TNBC group apply.

General Considerations

Data will be summarized and/or analyzed by cohort. Safety and demographic data will be summarized using standard tabulations and listings. Continuous variables will be summarized using descriptive statistics such as mean, standard deviation, median, minimum value, and maximum value. Continuous variables may be summarized by a clinically relevant discretization, as appropriate. Categorical variables will be summarized using frequency counts and percentages. Time-to-event data will be summarized using the Kaplan-Meier method. All time to event endpoints are measured from day of enrollment (Day-2 pretreatment baseline visit). Where appropriate, 95% confidence intervals around point estimates will be presented, and estimates of the median and other quantiles, as well as individual time points (e.g., 3-month, 6-month, and 12-month rates), will be produced. Data will be provided in data listings.

Objective response rate will be reported with category counts, percentage and 95% confidence interval. Duration of response (DOR), TTR, and OS will be evaluated using Kaplan-Meier estimates and curves will be generated based on these estimates.

SELLAS Life Sciences Group

Protocol: SLS17-201/MK3475-770 Protocol v1.1 (Amendment 1.0)

Galinpepimut-S

12 April 2019

Date of Protocol 12 April 2019
Amendment:

List of Abbreviations

Abbreviation	Definition
aa	amino acids
AE	adverse event
AGO-OVAR	Arbeitsgemeinschaft Gynaekologische Onkologie - Studiengruppe Ovarialkarzinom
allo-SCT	allogenic (hematopoietic) stem cell transplant
ALT	alanine aminotransferase
AML	acute myeloid leukemia
ANC	absolute neutrophil count
APC	antigen-presenting cell
APL	acute promyelocytic leukemia
aPTT	activated partial thromboplastin time
AST	aspartate aminotransferase
AUC	area under the concentration curve
BCG	Bacillus Calmette–Guérin
BICR	Blinded Independent Central Review
BM	bone marrow
BP	blood pressure
CBC	complete blood count
CBFB/MYH11	core-binding factor beta subunit/myosin heavy chain-11
cDNA	complementary deoxyribonucleic acid
CFR	Code of Federal Regulations
C _{max}	maximum observed concentration
CML	chronic myeloid leukemia

Abbreviation	Definition
CNS	central nervous system
CR	complete remission, complete response (AML)
CR1	first complete remission (AML)
CR2	second complete remission (AML)
CRC	colorectal cancer
CrCl	creatinine clearance
CRi	CR with incomplete recovery of blood counts (AML) (encompasses the definition of CRp)
CRi/CRp	CR with incomplete recovery of blood counts or platelets (AML)
CRO	clinical research organization
CRp	CR with incomplete recovery of blood platelets (AML)
CT	computed tomography
CTCAE	Common Terminology Criteria for Adverse Events
CTL	cytotoxic T-lymphocyte
CV	coefficient of variation
DFS	disease free survival
DILI	drug-induced liver injury
DLT	dose-limiting toxicity
DMC	data monitoring committee
DNA	deoxyribonucleic acid
DOR	duration of response
DTH	delayed-type hypersensitivity testing

Abbreviation	Definition
ECG	electrocardiogram
ECI	Events of Clinical Interest
eCRF	electronic case report form
ECOG	Eastern Cooperative Oncology Group
EDC	electronic data capture
EDTA	ethylene diamine tetra-acetic acid
EFS	event free survival
ELISPOT	enzyme-linked immunospot
ELN	European LeukemiaNet
EOT	end-of-treatment
ES-SCLC	extensive stage small cell lung cancer
FAS	full analysis set
FDA	Food and Drug Administration
FIR	First Interpretable Results
FISH	fluorescence in situ hybridization
FN	febrile neutropenia
FT3	free triiodothyronine
FT4	free thyroxine
GBM	glioblastoma multiforme
gBRCA mut	germline BRCA mutations
GCP	Good Clinical Practice
G-CSF	granulocyte colony-stimulating factor
GFR	glomerular filtration rate

Abbreviation	Definition
GM-CSF	granulocyte-macrophage colony-stimulating factor
GOG	Gynecologic Oncology Group (US)
GPS	galinpepimut-S
H	hour
HBsAg	hepatitis B surface antigen
HCV RNA	hepatitis C RNA
HER2	human epidermal growth factor receptor 2
HIPAA	Health Insurance Portability and Accountability Act
HIV	human immunodeficiency virus
HLA	human leukocyte antigen
HMA	hypomethylating agent
HSCT	hematopoietic stem cell transplant
IB	Investigator's Brochure
ICF	informed consent form
ICH	International Council on Harmonisation
iCPD	iRECIST confirmed progressive disease
ICS	intracellular cytokine staining
ICU	intensive care unit
IDH1	isocitric dehydrogenase-1
IEC	independent ethics committee
IHC	immunohistochemical
ILD	Interstitial lung disease

Abbreviation	Definition
INR	International Normalized Ratio
IR	immune response
irAE	immune-related adverse event
IRB	Institutional Review Board
iRECIST	Immune-related Response Evaluation Criteria In Solid Tumors
IRR	infusion related reaction
IRS	immuno-reactive score
ISR	injection site reaction
ITT	intent-to-treat
IV	intravenous
IWRS	interactive web response system
LFS	leukemia-free survival
LRV	lower reference value
LSC	leukemic stem cell
mAb	monoclonal antibody
MCC	Moffitt Cancer Center
MDS	myelodysplastic syndrome
MedDRA	Medical Dictionary for Regulatory Activities
MDSC	Myeloid-derived suppressor cell
MHC	major histocompatibility complex
mITT	modified intent-to-treat
MK-3475	pembrolizumab
MM	multiple myeloma

Abbreviation	Definition
MOA	mechanism of action
MPM	malignant pleural mesothelioma
MRD	minimal residual disease
MRI	magnetic resonance imaging
MRK	Merck & Co., Inc., Kenilworth, N.J., USA (known as MSD outside the United States and Canada)
MS	microsatellite
MSI	microsatellite instability
MSKCC	Memorial Sloan-Kettering Cancer Center
MSS	microsatellite stable
NCI	National Cancer Institute
NCI CTCAE	National Cancer Institute Common Toxicity Criteria for Adverse Events
NIH	National Institutes of Health
NSAID	non-steroidal anti-inflammatory drug
NSCLC	non-small cell lung cancer
NYHA	New York Heart Association
ORR	overall response rate
OS	overall survival
OvC	ovarian cancer
PARP	poly-ADP ribose polymerase
PB	peripheral blood
PCR	polymerase chain reaction

Abbreviation	Definition
PD	progressive disease
PD-1	programmed cell death receptor 1
PFS	progression-free survival
PK	pharmacokinetics
PD-L1	ligand to PD-1 receptor
PML-RAR- α	promyelocytic leukemia-retinoic acid receptor alpha
PPS	per-protocol set
PR	partial response
PT	Prothrombin time
PTT	Partial thromboplastin time
Q2W	every 2 weeks
Q3W	every 3 weeks
RBC	red blood cell
RECIST	Response Evaluation Criteria In Solid Tumors
RT-PCR	reverse transcription polymerase chain reaction
SAE	serious adverse event
SAF	safety analysis set
SAP	statistical analysis plan
SC	subcutaneous
SCLC	small cell lung cancer
SCT	stem cell transplant
SD	standard deviation
SIM	Site Imaging Manual

Abbreviation	Definition
SUSAR	suspected unexpected serious adverse reaction
SWFI	sterile water for injection
T _{1/2}	terminal elimination phase half-life
T1DM	Type 1 diabetes mellitus
T3	triiodothyronine
TAA	tumor-associated antigens
TAM	tumor-associated macrophage
TBX	tumoral biopsy samples
TEAE	treatment-emergent adverse event
T _{max}	time at which the highest drug concentration occurs
TME	tumor microenvironment
TNBC	triple-negative breast cancer
TRAE	treatment related adverse events
Treg	T-regulatory cell
TSH	thyroid stimulating hormone
TTR	time to response
TV	target value
ULN	upper limit of normal
US	United States
USP	United State Pharmacopeia
WBC	white blood cell
WOCBP	woman of childbearing potential
WT1	Wilms tumor gene

1 Introduction

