1.3.1.2.3. Small Cell Lung Cancer (Second Line)

Treatment options for patients with SCLC who progress on platinum-based chemotherapy are limited. WT1 expression has not been studied in SCLC as extensively as in NSCLC, mainly due to the relative rarity of the former. Nonetheless, WT1 positivity is higher (40 to 83%) in SCLC versus NSCLC (Babiak et al, 2014; Menssen et al, 2000; Oji et al, 2002;

Wang et al, 2013). Therefore, WT1 is an appropriate target for direct TAA-specific immunotherapy approaches, such as galinpepimut-S. Pembrolizumab, an anti-PD-1 monoclonal antibody designed to block the interaction between PD-1 and its ligands PD-L1 and PD-L2, has shown antitumor activity in multiple advanced malignancies, including thoracic tumors such as NSCLC and SCLC (<http://meetinglibrary.asco.org/record/109650/abstract>).

The median PFS and OS following initial chemotherapy in extensive stage small cell lung cancer (ES-SCLC) patients are 2 and 7 months, respectively (Ready, 2015). Maintenance therapy with pembrolizumab did not improve PFS in these patients but favorable OS suggests that some SCLC patients can benefit from maintenance pembrolizumab (Clinical trial information: NCT02359019; http://abstracts.asco.org/199/AbstView_199_183991.html). In patients with PD-L1+ SCLC who have progressed on prior platinum-based therapy, pembrolizumab is generally well tolerated and has promising antitumor activity. Enrollment in the SCLC cohort of KEYNOTE-028 is ongoing (Clinical trial information: NCT02054806). The activity of anti-PD1 agents in SCLC in the second line of therapy is reflected in ORR values of about 33 to 37% (Ott et al, 2016; Hellman et al, 2016; Antonia et al, 2016; Riess et al, 2016). In view of the above, there is good rationale to investigate the combination of galinpepimut-S plus pembrolizumab in SCLC.

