6.8.2. Tumor Imaging During the Study

For solid tumors only, the first on-study imaging assessment should be performed at Week 9 (Day 1 \pm 7 days) from the date of enrollment. Subsequent tumor imaging should be performed at Weeks 18, 27, 36, 45, 54, 63, 72, and 84 (Day 1 \pm 7 days) or more frequently if clinically indicated. Imaging timing should follow calendar days and should not be adjusted for delays in cycle starts. Imaging should continue to be performed until disease progression is identified by the investigator.

Objective response should be confirmed by a repeat imaging assessment. Tumor imaging to confirm PR or CR should be performed at least 4 weeks after the first indication of a response is observed. Patients will then return to regular scheduled imaging, starting with the next scheduled imaging time point. Patients who receive additional imaging for confirmation do not need to undergo the next scheduled tumor imaging if it is less than 4 weeks later; tumor imaging may resume at the subsequent scheduled imaging time point.

Per iRECIST ([Section 6.8.5](#)), disease progression should be confirmed by the site 4 to 8 weeks after.

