7.6.1. Analysis of Primary Efficacy Endpoint

For each tumor-specific cohort, a Bayesian approach with non-informative Jeffreys prior beta distribution with parameters $a = 0.5$ and $b = 0.5$ will be used to estimate the ORR and its 95% credible interval based on the posterior distribution.

At the time of analysis, within each tumor-specific cohort, the prior distribution will be updated with all available data to obtain the posterior distribution of the true ORR. The posterior probabilities that ORR exceeds TV and LRV will be reported for each cohort. A high posterior probability that $ORR > LRV$ will support a “Go” decision to continue development in the cohort, and a low posterior probability that $ORR > TV$ will support a “Stop” decision to halt development in the cohort. A “Consider” decision results if neither a Stop nor a Go decision can be made. The specific criteria for making a Stop, Consider, or Go decision within each tumor-specific cohort are derived using the following acceptable risks:

- 10% false stop risk: maximum acceptable probability that $ORR > TV$ given that a Stop decision is made.

- 20% false go risk: maximum acceptable probability that $ORR \leq LRV$ given that a Go decision is made

Before reaching the planned sample size in a cohort, the posterior probabilities will be updated continuously after each patient or group of patients and will be used to determine, within each cohort, the predictive probability of eventually reaching a Stop decision at the planned sample size. If this predictive probability is $\geq 80\%$, then enrollment in that cohort may be stopped early for futility. Definitions of the decision boundaries can be found in [Section 7.6.6](#).

In general, Stop/Go and futility decision criteria are non-binding and may be regarded as guidance and information to be integrated with a full medical review of safety and efficacy data observed at the time of analysis in determining the next course of action.

No tests of statistical significance are planned.

Patients with missing ORR will be conservatively classified as non-responders for the primary analysis.

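### In the solid-tumor cohorts, the exploratory mITT set keeps unscanned clinical progressors but drops patients who die before the first scan, so any such death raises the mITT response rate

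*Combined protocol and SAP*

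**What the plan says.** The analysis sets are defined in the synopsis (Statistical Methods, Analysis Sets) and again in Section 7.5.

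- **mITT.** Assigned patients must "have at least 1 post-baseline efficacy assessment (RECIST 1.1), even if they deviate from the protocol in any major way". The only route in without a scan is the added sentence: "The mITT will also include any patient that goes off study treatment because of clinical progression prior to the first scheduled per-protocol scan".
- **PPS.** Patients must "have at least 1 post-baseline efficacy assessment (RECIST 1.1), and do not deviate from the protocol in any major way", with no exception for those never scanned.
- **Role of the sets.** "All efficacy analyses will be based on the FAS and will also be conducted on the mITT set and PPS for exploratory purposes".
- **Missing response.** Section 7.6.1: "Patients with missing ORR will be conservatively classified as non-responders for the primary analysis".
- **Timing.** Section 6.8.2, for solid tumors: "the first on-study imaging assessment should be performed at Week 9".

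The synopsis (Procedures) lists progression and death as separate ends of treatment, so death cannot simply be read into the clinical-progression exception. Section 4.2.3 allows no replacements.

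**The concern.** The mITT exception shows that the plan recognised the problem: if a scan is required, patients who fail early fall out of the denominator. It closes the gap for one kind of early failure and leaves it open for another. A patient taken off treatment for clinical progression in Week 5 stays in mITT as a non-responder. A patient who dies in Week 5 while still on treatment, from disease or toxicity, drops out.

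Membership then depends on surviving to a scan, which is an outcome after treatment starts. Section 6.8.2 asks that a response be confirmed by repeat imaging at least 4 weeks after it is first seen, so a patient with no scan cannot be a responder. Each exclusion shrinks the denominator and leaves the numerator alone. Secondary and exploratory efficacy analyses are also repeated on mITT. OS and PFS are exploratory endpoints, and the synopsis measures time-to-event endpoints from enrollment, so an mITT survival curve would start at enrollment but omit some early deaths.

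What is at stake is how far a supportive result can be trusted. The primary result does not depend on it.

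**Working it through.** **Inputs.** Cohort sizes, LRV and TV: Section 7.4. Prior Beta(0.5, 0.5), 20% false-go risk and 10% false-stop risk: Section 7.6.1. Boundaries: Table 14. The number of unscanned deaths, k, is not in the documents; k = 1 to 3 is an assumption.

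**Step 1: reproduce the plan's boundaries.** With x responders of n, the posterior is Beta(0.5 + x, 0.5 + n − x). Go is the smallest x with P(ORR > LRV) ≥ 0.80. Stop is the largest x with P(ORR > TV) ≤ 0.10. This returns Go/Stop counts of 4/1 (CRC, OvC), 8/5 (SCLC) and 4/1 (TNBC, AML), as in Table 14. Exact binomial sums give 58.9% Go and 6.9% Stop at a true ORR of 20% in CRC or OvC, against 59% and 7% in Table 11.

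**Step 2: effect on the observed rate.** Dropping k unscanned deaths changes x/n to x/(n − k), a relative rise of n/(n − k). For SCLC with 8 responders:

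| Dropped | Rate |
|---|---|
| 0 | 8/20 = 40.0% |
| 1 | 8/19 = 42.1% |
| 2 | 8/18 = 44.4% |
| 3 | 8/17 = 47.1% |

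**Step 3: effect on the posterior, one responder short of Go.** CRC figures assume that all 20 patients are MSS or MSI-L.

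| Cohort | Dropped | Rate | P(ORR > LRV) |
|---|---|---|---|
| CRC or OvC | 0 | 3/20 = 15.0% | 0.786 |
| CRC or OvC | 1 | 3/19 = 15.8% | 0.810 |
| SCLC | 0 | 7/20 = 35.0% | 0.696 |
| SCLC | 2 | 7/18 = 38.9% | 0.798 |
| SCLC | 3 | 7/17 = 41.2% | 0.843 |
| TNBC | 0 | 3/15 = 20.0% | 0.726 |
| TNBC | 1 | 3/14 = 21.4% | 0.765 |
| TNBC | 2 | 3/13 = 23.1% | 0.802 |

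If the mITT posterior were set beside the 0.80 level, one dropped patient would carry 3 responders past it in CRC or OvC. It would take two in TNBC and three in SCLC.

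**Step 4: with the deaths counted.** The mITT denominators return to 20 or 15 in these examples. The rates and posteriors return to the rows with none dropped, which are also the FAS values.

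**The case against.** The strongest answer is that the decision analysis already handles this. The FAS holds every assigned patient, missing response counts as non-response, mITT is labelled exploratory, and no significance tests are planned. All of that stands, and it limits the point to a supportive set.

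Several stronger readings are tempting, and the documents do not support them.

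- **That early deaths are hidden.** Patients who received any study drug stay in the safety set. Section 7.6.4.1 tabulates serious events including death, and Grade 5 toxicity counts as a DLT. Sections 5.3.6.1 and 5.3.6.2 include a stopping rule for attributable deaths. The synopsis and Section 6.3 also follow PFS and OS by the ITT principle.
- **That about a fifth of SCLC patients would be dropped.** A reader might take the 7-month median OS in Section 1.3.1.2.3, assume a constant hazard, and get 1 − 0.5^(9/(7 × 4.348)) = 18.5% dead by Week 9, or 3.7 of 20. That section describes "The median PFS and OS following initial chemotherapy in extensive stage small cell lung cancer", not this second-line combination in patients selected for ECOG 0 or 1. The figure also counts patients who first left for progression, and mITT keeps those.
- **That a Stop result could look like success.** At the SCLC Stop count, 5/16 = 31.3% exceeds the 30% LRV only with 4 dropped, more than that 3.7. With 3 dropped, 5/17 = 29.4%. Even at 5/16, P(ORR > 30%) is 0.56, well short of 0.80.
- **That the PPS response rate can only be too high.** The PPS also removes major deviators, who may be responders, so it can move either way.
- **That Go/Stop itself is biased.** The synopsis says "the prior distribution will be updated with all available data from the evaluable patients to obtain the posterior distribution of the true ORR", and evaluable is undefined. Section 7.6.1 refers to all available data with missing response as non-response, and the FAS is the stated basis, so the text does not establish that the decision uses mITT.

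It is also fair to say that Section 6.8.3 asks for a scan at discontinuation, which would bring many toxicity stoppers into mITT. It cannot bring in deaths.

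**Conclusion.** The gap is real and narrow. As written, mITT excludes solid-tumor patients who die unscanned before the first post-baseline assessment without having left treatment for clinical progression. If any occur, the mITT response rate is higher than it would be with them counted, and mITT survival summaries lose early deaths. If none occur, these deaths cause no distortion.

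For 1 to 3 such patients in a cohort of 20, the relative rise is 5% (20/19) to 18% (20/17). These counts are illustrative, because the documents support no estimate of how many to expect. The FAS primary analysis, the boundaries in Table 14, the probabilities in Tables 11 to 13 and the safety set are unaffected.

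The point is limited to solid tumors. AML is not assessed by RECIST, so the entry condition does not fit that cohort and these figures do not describe it.

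**What to change.** In Section 7.5 and in the synopsis, extend the mITT exception so that the set also includes, as a non-responder, any patient who dies from any cause, or stops treatment, before the first post-baseline assessment. Naming those who stop treatment matters, because an unscanned patient who stops for toxicity or withdraws creates the same bias and a discontinuation scan may not be obtained.

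The cost is one sentence in each place, with no new data collection and no change to sample size or boundaries. The downside is an mITT response rate that is slightly less favourable and closer to the FAS rate.

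Changing the PPS is optional and not required. Requiring an assessment is a common feature of a per-protocol set, and the FAS carries the conclusion.
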